ratio of change from baseline of standing height at 6 months or 12 months of a patient taking recifercept to a matched subject in the concurrent external control. The null hypothesis is the median value (ie, 50 percentile) of the aforementioned ratio is equal to 1.

A table and figure presented below displays the number of pairs required to detect the median ratio (denoted as φ) under the alternative hypothesis.

Type I error	Power	Number of Pairs to detect φ					
		φ=1.5	$\phi = 2$	φ=2.5	$\phi = 3$	φ=3.5	$\phi = 4$
.05	.8	88	22	10	6	4	3
.05	.9	115	29	13	8	5	4
.1	.8	71	18	8	5	3	2
.1	.9	96	24	11	6	4	3
.2	.8	55	14	7	4	3	2
.2	.9	77	20	9	5	4	3

Table 1. Sample size and power calculation

Data analysis

Descriptive statistics will be tabulated on patient demographic and baseline clinical characteristics between achondroplasia patients from Study C4181005 and patients from Study C4181001 who meet all the inclusion and exclusion criteria of Study C4181005. To construct a concurrent external control for Study C4181005, a propensity score (PS) will be created to achieve balance across covariates between achondroplasia patients from Study C4181005 and patients from Study C4181001 who meet all the eligibility criteria of Study C4181005. The PS will be estimated using standard logistic regression approaches with the "outcome" variable being the data source (whether patients were included in Study C4181005 and exposure to recifercept treatment) and the predictors being the variables associated with both the exposure (recifercept treatment) and the outcomes of interest (i.e. height growth). This model will provide the predicted probability of being in the trial cohort relative to the concurrent external control cohort as a function of the covariates (the propensity score of being included in Study C4181005). The potential covariates may include demographics (e.g. age, gender, race and ethnicity), clinical characteristics (e.g. presence of achondraplasia-related complications, Tanner stage, and other non-achondroplasia-related conditions of medical significance). The distribution of the PS will be reviewed and patients with a PS in the areas of nonoverlap and/or with extreme PS values might be excluded to improve validity (PS trimming). Each patient in the PS trimmed receifercept group will be

PFIZER CONFIDENTIAL

CT24-WI-GL02-RF02 3.0 Non-Interventional Study Protocol Template For Secondary Data Collection Study 23-May-2022 Page 11 of 26

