matched on a ratio of 1:1 with patients in the PS trimmed concurrent external control using optimal nearest neighbour matching with a maximum caliper of 1%. Pre- and post-matching balance will be assessed using standardized differences between these two PS-matched groups. A negative control outcome may also be identified to evaluate the pre- and post-matching balance.

After the concurrent external control is constructed by PS matching, descriptive statistics will be tabulated on patient demographic and baseline clinical characteristics between achondroplasia patients from PS-matched recifercept phase 2 trial cohort and those from PS-matched concurrent external control. Two-sample T-tests will be used for continuous variables, and chi-square tests for categorical variables assuming the distribution is normal. Frequency of primary, secondary **CC** outcomes of interest and 95% confidence intervals will be computed.

Hazard ratios and associated 95% confidence intervals of dichotomous outcomes (including height growth in the achondroplasia reference population +50%, and occurrence of selected achondroplasia-related complications) in PS-matched groups will be estimated by multivariable cox proportional hazards regression models. The effect of recifercept on continuous outcomes (including height growth, anthropometric measures, CCL

in PS-matched groups will be estimated by linear mixed

models.

To maximize the number of patients in the trial cohort and the concurrent external control cohort included in this pilot project, additional methods will be explored. Coarsened weighting and full matching may be explored. Other than matching, inverse probability weight (IPW) and/or the fine stratification weighting may also be used to balance the key covariates between patients in the concurrent external control cohort (patients in C4181001 who meet the inclusion and exclusion criteria of Study C4181005) and patients in Study C4181005 (details of these methods will be outlined in the SAP).

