9.6. Data analysis

A single pooled dataset will be released for analysis. The release will occur when for selected, targeted data (in Table 3): a) review and documentation of relevant CRF and non-CRF data; and b) all open queries are resolved. There will be two releases of data. The first release coincides with approximately 30 pairs of patients – that is, a patient from C4181001 matched to a patient from C4181005 – having 6 months of growth data. The second release will take place at the beginning of the interim analysis for C4181005. There may be an additional release of data from both studies that coincides with the completion of C4181005.

Descriptive statistics will be tabulated on patient demographic and baseline clinical characteristics between achondroplasia patients from Study C4181005 and patients from Study C4181001 who meet all the inclusion and exclusion criteria of Study C4181005. To construct a concurrent external control for Study C4181005, a propensity score (PS) will be created to achieve balance across covariates between achondroplasia patients from Study C4181005 and patients from Study C4181001 who meet all the eligibility criteria of Study C4181005. The PS will be estimated using standard logistic regression approaches with the "outcome" variable being the data source (whether patients were included in Study C4181005 and exposure to recifercept treatment) and the predictors being the variables associated with both the exposure (recifercept treatment) and the outcomes of interest (i.e. height growth). This model will provide the predicted probability of being in the trial cohort relative to the concurrent external control cohort as a function of the covariates (the propensity score of being included in Study C4181005). The potential covariates may include demographics (e.g. age, gender, race and ethnicity), clinical characteristics (e.g. presence of achondraplasia-related complications, Tanner stage, and other nonachondroplasia-related conditions of medical significance). The distribution of the PS will be reviewed and patients with a PS in the areas of nonoverlap and/or with extreme PS values might be excluded to improve validity (PS trimming). Each patient in the PS trimmed receifercept group will be matched on a ratio of 1:1 with patients in the PS trimmed concurrent external control using optimal nearest neighbour matching with a maximum

PFIZER CONFIDENTIAL

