3.2 STATISTICAL DECISION RULES

The alpha level will be 0.05, 2-sided. No adjustments for multiple comparisons will be made.

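### Protocol Table 1: the pair numbers for φ = 2 to 4 are a large-sample rescaling of the φ = 1.5 column, so the stated 80–90% power is wrong for the smallest entries

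*Protocol*

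**What the plan says.** Study size is set out in the Protocol Abstract (Study size, with Table 1) and again in Section 9.4 (with Figure 1, not available here). The quantity sized is described as "ratio of change from baseline of standing height at 6 months or 12 months of a patient taking recifercept to a matched subject", the match coming from the external control group. The hypothesis is worded as follows: "The null hypothesis is the median value (ie, 50 percentile) of the aforementioned ratio is equal to 1".

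The content of Table 1 is introduced in these words: "A table and figure presented below displays the number of pairs required to detect the median ratio". It covers φ from 1.5 to 4, at type I error .05, .1 and .2 and power .8 and .9. Neither place names the test, whether it is one- or two-sided, the distribution of the ratio or its spread. One table serves both 6 and 12 months.

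Two other passages bear on it. Protocol Section 9.6 states: "The first release coincides with approximately 30 pairs of patients" with 6 months of growth data. The SAP no longer tests the median ratio. Section 1 drops height growth, Section 3.1 tests mean change in height Z-score, Section 3.2 states "The alpha level will be 0.05, 2-sided", and Section 7.2 uses a mixed model. The SAP as supplied contains no new sample-size calculation.

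**The concern.** Several cells promise 80% or 90% power for a hypothesis about a median with 2 to 5 pairs. The usual one-sample tests of a median cannot produce a small p-value from so few observations. The regular fall along each row also suggests one large-sample formula applied well outside its range.

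These are the only power figures in the two documents. The project is a pilot meant to inform the design of a pivotal trial, so a reader who takes the right-hand columns at face value would think a handful of matched pairs could suffice. The table also does not show what can be detected with the pairs that can actually be formed.

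**Working it through.** **Inputs.** Table 1, transposed (each column here is one row of the protocol's table, headed alpha/power):

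| φ | .05/.8 | .05/.9 | .1/.8 | .1/.9 | .2/.8 | .2/.9 |
|---|---|---|---|---|---|---|
| 1.5 | 88 | 115 | 71 | 96 | 55 | 77 |
| 2 | 22 | 29 | 18 | 24 | 14 | 20 |
| 2.5 | 10 | 13 | 8 | 11 | 7 | 9 |
| 3 | 6 | 8 | 5 | 6 | 4 | 5 |
| 3.5 | 4 | 5 | 3 | 4 | 3 | 4 |
| 4 | 3 | 4 | 2 | 3 | 2 | 3 |

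The trial has 63 treated children (Abstract, Study design), and the first release is at about 30 pairs (Section 9.6).

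**Step 1: reproduce the table.** Take n(φ) = n(1.5) × 0.25/(φ−1)², rounded up. First row of Table 1 (.05/.8): 88 × 0.25 = 22. Dividing 22 by 1, 2.25, 4, 6.25 and 9 gives 22, 9.78, 5.5, 3.52 and 2.44, so 22, 10, 6, 4 and 3, as printed. Second row (.05/.9): 28.75, 12.78, 7.19, 4.6 and 3.19, so 29, 13, 8, 5 and 4, as printed. The other four rows also agree, so all 30 entries for φ = 2 to 4 are reproduced. Column φ = 1.5 is the base. It cannot be derived from the documents, because they give no test or spread.

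**Step 2: can the small cells reject at all?** Without ties, the smallest p-value of a sign or signed-rank test with n pairs is 2^(1−n) two-sided and 2^(−n) one-sided.

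| pairs | two-sided | one-sided |
|---|---|---|
| 2 | 0.5 | 0.25 |
| 3 | 0.25 | 0.125 |
| 4 | 0.125 | 0.0625 |
| 5 | 0.0625 | 0.03125 |
| 6 | 0.03125 | 0.015625 |

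The 15 cells with 5 pairs or fewer, each against its own alpha:

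| alpha | entries ≤ 5 | cannot reject, two-sided | cannot reject, one-sided |
|---|---|---|---|
| .05 | 4, 3, 5, 4 | 4, 3, 5, 4 | 4, 3, 4 |
| .1 | 5, 3, 2, 4, 3 | 3, 2, 4, 3 | 3, 2, 3 |
| .2 | 4, 3, 2, 5, 4, 3 | 3, 2, 3 | 2 |
| total | 15 | 11 | 7 |

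All 11 are at φ = 3.5 or 4. The four cells that can reject two-sided need every ratio on the same side of 1. To have the stated power there, the probability that a single ratio exceeds 1 must lie between 0.8^(1/4) = 0.946 and 0.9^(1/5) = 0.979.

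**Step 3: would a t-test rescue alpha .05?** Assume a two-sided z formula lies behind each row. The implied SD is then √(0.25 × n(1.5))/(z for alpha/2 + z for power).

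- Power .8: √22/2.8016 = 1.674. Power .9: √28.75/3.2415 = 1.654.
- Noncentrality is (φ−1)√n/SD, on n−1 degrees of freedom.

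| stated power | φ | pairs | noncentrality | critical t | t-test power |
|---|---|---|---|---|---|
| 80% | 3.5 | 4 | 2.99 | 3.182 | 53% |
| 80% | 4 | 3 | 3.10 | 4.303 | 41% |
| 90% | 3.5 | 5 | 3.38 | 2.776 | 72% |
| 90% | 4 | 4 | 3.63 | 3.182 | 68% |

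**Step 4: what attainable numbers detect.** By the table's own scaling at alpha .05 and 80% power, φ = 1 + √(22/n): about 1.86 for 30 pairs, 1.66 for 50 and 1.59 for 63. These values inherit the table's unstated assumptions.

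**The case against.** The strongest reply is that nothing depends on the faulty cells. They sit at a 3.5- to 4-fold growth ratio that the plan never adopts, the earliest release is at about 30 pairs, and the SAP has moved to another hypothesis and model. That stands, and it limits the weight of the point. It does not make the printed power correct.

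The protocol also names no sign or signed-rank test; Section 9.6 plans linear mixed models for continuous height growth. So the impossibility is conditional on the test, and the count depends on sidedness: the SAP's two-sided level belongs to a different hypothesis. The t-test figures are conditional too. The implied SD is not the same in every row (about 1.65 at .05/.9, about 1.75 at .2/.8). SAP Section 1 says the height-growth ratio would lead to a Cauchy variable, which has no SD. At alpha .2 with 90% power the same t-test calculation gives 85%, 88% and 85% for 5, 4 and 3 pairs, close to the stated figure.

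A reader might infer more than the documents support:

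- That no entry of 2 to 5 pairs can reach significance. Two-sided, 5 pairs can reach .1, and 4 or 5 pairs can reach .2: four of the 15 cells can reject. One-sided, eight can.
- That the φ = 1.5 entries above 63 (71, 77, 88, 96, 115) are errors. The table is a grid of requirements; it does not claim that so many pairs exist.
- That the release at about 30 pairs was chosen from the table's 29 pairs for φ = 2. No passage links them.

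**Conclusion.** The point holds for the smallest entries. That the 30 entries for φ = 2 to 4 rescale the first column is exact arithmetic. The zero power of 11 of the 15 cells with 5 pairs or fewer assumes a two-sided sign or signed-rank test without ties; one-sided the count is 7, and both 2-pair cells fail either way. The shortfall at alpha .05 under a t-test (41% to 72% where 80% to 90% is stated) assumes a two-sided z formula behind the first column and a roughly normal ratio.

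The error is in the protocol's power statement, not in any adopted sample size. It should be corrected because it is the only such statement in the documents and protocol v1.1 still carries it.

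**What to change.** The simpler course is to withdraw Table 1 and Figure 1 and mark them as superseded by the SAP's height Z-score hypothesis. Otherwise, replace them with the detectable effect at attainable pair numbers, for example 30, 50 and at most 63. Compute it for the analysis actually planned, and state the test, sidedness and assumed spread, separately for 6 and 12 months where they differ. The replacement should not presume a sign or signed-rank test, since neither document plans one.

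If the median-ratio table is kept, name its test, recompute it with an exact or small-sample method, and remove cells that cannot reach significance at their own alpha.

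The cost is protocol text and at most one recalculated table and figure, with less favourable numbers. No data collection changes.

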5. AMENDMENTS AND UPDATES

Amendment number	Date	Protocol section(s) changed	Summary of amendment(s)	Reason
1.1	Nov 09, 2023	Milestones	Realigned end of data collection date; Updated CSR approval date to be 11 months after end of data collection, and BR tables to be 12 months after end of data collection.	Recifercept discontinued, never reached POC; hence not a Pfizer authorized product, not subject to Article 46, and CSR approval deadline should be 11 months after end of data collection date not 6 months; BR tables deadline should be 12 months after end of data collection. Team agreed, [name] suggested to do protocol administrative amendment.

6. MILESTONES

Milestone	Timeline
Study Protocol	May 2022
Statistical analysis plan	June 2022
Start of data collection	October 2022
End of data collection	May 2023
Data analysis and internal study report	April 2024
Basic Results tables for CT.gov	May 2024

7. RATIONALE AND BACKGROUND

Achondroplasia is a heritable autosomal dominant disorder and is the most common form of skeletal dysplasia in humans, with a global birth prevalence of 1 in 25-30,000 or ~250,000 individuals worldwide (1–3). Achondroplasia is caused by a single-point gain-of-function mutation in the gene encoding the fibroblast growth factor receptor 3 (FGFR3) (2,4). FGFR is a key inhibitory regulator of endochondrial ossification and its over-activiation interferes with normal chondrocyte maturation and causes shorter long bones and changes in flat bones such as the occipital bone and vertebrae.

PFIZER CONFIDENTIAL CT24-WI-GL02-RF02 3.0 Non-Interventional Study Protocol Template For Secondary Data Collection Study 23-May-2022 Page 13 of 26

Achondroplasia results in short stature and a range of severe complications due to abnormal ossification centers in the cranial base, facial bones, vertebrae, rib cage, and joints. Lordosis, kyphosis, small foramen magnum, and spinal stenosis are the most common achondroplasia-related orthopaedic complications. Other achondroplasia related complications include sleep-disordered breathing, otitis media, and hydrocephalus. Medical complications associated with achondroplasia greatly impact physical and psychosocial functioning, self-esteem, and patient quality of life (3,5).

Currently, vosoritide is the only treatment approved by EMA (for achondroplasia patients aged 2 years and older with open growth plates) and FDA (for achondroplasia patients aged 5 years and older with open growth plates) to increase linear growth. It is an analog of C-type natriuretic peptide and works by binding to a receptor called natriuretic peptide receptor type B (NPR-B), which reduces the activity of FGFR3. Other available treatments are either aimed at limb lengthening with surgery or are interventions to treat the complications associated with achondroplasia. Recifercept is a modified soluble recombinant human FSFR3 under development for the treatment of achondroplasia. Recifercept is designed to be a decoy protein, competing for ligands of the FGFR3-G380R receptor responsible for achondroplasia and by forming inactive heterodimers with FGFR3 monomers. By binding free FGFR3-activating ligands and forming inactive dimers, recifercept reduces activation of the receptor, allowing chondrocyte proliferation and differentiation to proceed.

A recifercept phase 2 clinical study (Study C4181005) is ongoing to investigate the safety, tolerability, pharmacokinetics (PK) and efficacy of recifercept in children aged 3 months to 10 years with achondroplasia. Fifty-four eligible participants aged 2-10 years and 9 patients aged 3 months to 2 years will be enrolled and randomized to receive one of three doses of recifercept subcutaneously (1mg/kg once-weekly, 2mg/kg twice weekly, or 1.5mg/kg once-daily, n=21 per dose). Once participants complete the phase 2 trial, they will be offered enrollment into an open-label extension study at the dose previously received in the phase 2 trial or at the therapeutic dose once it is identified. A separate multi-country prospective observational natural history study (Study C4181001) is ongoing to examine the anthropometric characteristics, and achondroplasia-related symptoms, tests, and treatments among children with achondroplasia. A total of 300 achondroplasia patients aged 0 and 15 years of age will be recruited and followed up for a duration of 5 years. All patients participating in Study C4181005 were or will be recruited from Study C4181001.

Objectives of this project are to evaluate the feasibility of constructing a concurrent external control for the recifercept phase 2 clinical trial (Study C4181005) using achondroplasia patients from the ongoing prospective natural history study (Study C4181001) and to compare selected outcomes of interest such as height growth, achondroplasia-related complications, and quality of life between achondroplasia patients in Study C4181005 and those in the concurrent external control. Ultimately, this project will assess the feasibility of leveraging the ongoing Study 4181001 as a concurrent external control arm for the recifercept pivotal trial.

Recifercept C4181010 NON-INTERVENTIONAL STUDY PROTOCOL V1.1, Nov 09, 2023 8. RESEARCH QUESTION AND OBJECTIVES

There are two research questions:

1) Can a concurrent external control for the recifercept phase 2 clinical trial be constructed using achondroplasia patients from a prospective observational natural history study?

2) What are differences in height growth, achondroplasia-related complications, patient functional status, and quality of life between patients enrolled in the recifercept phase 2 clinical trial and those in the concurrent external control?

Objectives of this pilot project include:

1. Construct a concurrent external control arm for recifercept phase 2 clincial trial using achondroplasia patients from a prospective observal natural history study

2. If objective #1 is met, the following will be compared to examine differences between patients enrolled in the recifercept phase 2 clincial trial and those in the concurrent external control:

- Height growth
- Selected anthropometric measurements, including but not limited to: standing height, sitting height, knee height, arm span, length of the legs, sitting height/standing height ratio, arm span to height/length difference, knee height/lower segment ratio
- Achondroplasia-related orthopaedic complications (including lordosis, kyphosis, small foramen magnum, spinal stenosis), and other achondroplasia-related complications (including apnea, AOM, and hydrocephalus)
- Differences in functional status and health-related quality of life

9. RESEARCH METHODS

9.1. Study design

This is a retrospective cohort study using existing data from two ongoing studies: C4181001 and C4181005. The study population will include two independent study cohorts: a) patients from Study C4181005 who have completed Visits 1 through 11 (at D183); b) patients from Study C4181001 who meet the eligibility criteria for Study C4181005 and have at least 6 months follow-up data. Eligible patients from Study C4181001 will be included as potential external controls for patients in Study C4181005, using propensity score methodology.

This pilot study has the potential to demonstrate the feasibility of Study C4181001 as concurrent external controls and provide viable study design options for the recifercept

pivotal trial. It will also provide information on the efficacy of recifercept compared to clinical practices in the real world. Having an external control arm in the trial allows for increased efficiency and decreased product development time.

9.2. Setting

This retrospective cohort study will include achondroplasia patients from Study C4181005 and those from Study C4181001 who meet the inclusion and exclusion criteria of Study C4181005. Study C4181005 is a single-arm trial to evaluate the safety and tolerability of recifercept doses and dosing regimen, and efficacy to increase height growth in achondroplasia patients. Study C4181005 will include approximately 63 children with achondroplasia aged 3 months to 10 years (inclusive) with Tanner Stage 1, who are enrolled and randomized to receive one of three doses of recifercept (1mg/kg once-weekly, 2mg/kg twice-weekly, or 1.5mg/kg once-daily) subcutaneously for 12 months. Demographics, medical history, anthropometric measurements, and patient-reported outcomes in functional status and quality of life are collected approximately every 3 months. Study C4181001 is a prospective natural history study to collect the longitudinal anthropometric and diseaserelated complication data in children with achondroplais. It will include approximately 300 achondroplasia patients aged 0-15 years with Tanner Stage I recruited from global sites. Patient data will be collected at baseline and at every 3-month interval visits, for a maximum of 5 years. Further details on data sources are presented in Table 1.

	Recifercept phase 2 Clinical Trial (Study C4181005)	Natural History Study (Study C4181001)
Study population	3m-10y, Tanner Stage 1	0-10y, Tanner Stage 1
Study duration	12 months	Up to 5 years
Visit interval	- Medical history collected at baseline	- Complications collected every 3 months
	- Anthropometric measurements every 3 months	- Anthropometric measures every 3 months
	- Biomarkers baseline, D1, D4, D8, D15, D29, M2, M3, M6, M9, M12	- Biomarkers sample taken once annually
	CCI	
Sample size	63 patients	300 patients anticipated
Primary objective	- Evaluate the safety and tolerability of recifercept doses and dosing regimens in participants aged ≥ 2 to <11 years with achondroplasia	- Collection of longitudinal anthropometric and disease-related complication data in children with achondroplasia

Table 2. Data sources*

PFIZER CONFIDENTIAL

CT24-WI-GL02-RF02 3.0 Non-Interventional Study Protocol Template For Secondary Data Collection Study 23-May-2022 Page 16 of 26

V 1.1, NOV 09, 2025		
	- Assess efficacy of recifercept to increase height growth in children with achondroplasia	
Secondary outcomes	- To evaluate the pharmacokinetics of recifercept in participants aged ≥ 2 to <11 years with achondroplasia	- Investigation of potential serum biomarkers in children with achondroplasia
	- To assess efficacy of recifercept to improve ahondroplasia-related complications	
	- To assess change in individual safety parameters	
CCI		
CCI		

